8.1.3 Efficacy Assessment

- Screening/Baseline Tumor Assessment: CT or MRI of brain, neck, chest, abdomen, pelvis, and all other known sites of disease within 28 days prior to randomization.

8.1.4 Patient Reported Outcome Assessment

- EORTC QLQ-C-30 must be completed before administration of first dose of Nivolumab.

9.1 TREATMENT/INTERVENTION PLAN

Nivolumab should begin within 14 days (+/-4 days) of randomization. The first day of Nivolumab is designated as study Day 1.

Arm 1: On Day 1, patients will receive a one hour infusion of Nivolumab 3mg/kg and then every 14 days (+/-2 days) until treatment progression per RECIST 1.1 criteria, unacceptable toxicity, or withdrawal of consent.

Arm 2: After randomization, patients will complete CT simulation. On Day 1 they will receive their first dose of Nivolumab (3mg/mg); they will receive their first radiation treatment (9 Gy) by study day 14. The additional 2 fractions of radiation (9 Gy per fraction) will be delivered within 10 business days, no more frequently than every other day. Nivolumab 3mg/kg will be administered

every 14 days (+/-2 days) until treatment progression per RECIST 1.1 criteria, unacceptable toxicity, or withdrawal of consent.

9.2 Intervention: Nivolumab

9.2.1 Preparation and Administration:

- Nivolumab injection is to be administered using a volumetric pump with a 0.2/1.2 micron pore size, low protein binding polyethersulfone membrane in-line filter at the protocol-specific doses.
- The line should be flushed at the end of the infusion with sufficient quantity of normal saline per institution SOC.
- Nivolumab is not to be administered as an IV push or bolus injection.
- At the dose of 3mg/kg, the total dose needed will be diluted to a minimum total volume of 60 ml in 0.9% Sodium Chloride or 5% dextrose injection solution.
- Care must be taken to assure sterility of the prepared solution as the product does not contain any anti-microbial preservative or bacteriostatic agent.
- Nivolumab should be administered over a 1-hour period; infusions will be controlled by a volumetric pump.
- Please refer to the current Investigator Brochure for further details.
- Allow the appropriate number of vials of Nivolumab to stand at room temperature for approximately 5 minutes before preparation.
- Ensure that Nivolumab solution is clear, colorless, and essentially free from particulate matter.
- Aseptically withdraw the required volume of Nivolumab into a syringe and dispense into an IV bag.
 - a. Add the appropriate volume of 0.9% Sodium Chloride injection solution.
 - b. Mix by gently inverting several times. DO NOT shake.
 - c. Record the Nivolumab expiration time and date on the IV bag label.
 - d. Attach the IV bag containing the Nivolumab solution to the infusion set, in-line filter, and infusion pump.
 - e. The infusion rate of the infusion pump should be adjusted to allow for a total infusion time of approximately 60 minutes.
 - f. At the end of the infusion period, flush the line with a sufficient quantity of 0.9% Sodium Chloride injection solution or 5% dextrose injection.
- Pharmacy supplies required:
 - a. Empty IV bags-50mg, 100mL, 200 mL
 - b. 0.9% NaCl bags
 - c. 0.2 or 0.22 micron in line filter and infusion tubing
 - d. Volumetric infusion pumps.

9.2.2 Selection and Timing of Dose for Each Subject

Subjects randomized to Arm 1 or Arm 2 will receive Nivolumab as a 60 minute IV infusion on Day 1 of the study. Subjects randomized to Arm 2 will receive their first radiation fraction by study day 14. Dose of Nivolumab is 3mg/kg and should be done based on the

body weight of the subject at the start of each cycle. If the subject's weight on the day of dosing differs by > 10% from the weight used to calculate the original dose, the dose must be recalculated. All doses should be rounded to the nearest milligram or as per institutional guidelines. There are no pre-medications recommended for Nivolumab.

9.2 Intervention: SBRT

9.2.1 Target Selection

- A single target lesion will be selected.
- The lesion must be safely amenable to irradiation in the judgment of the treating radiation oncologist; approval of PI is not required.
- Lesions must be located in one of the following eight locations:
 - Central Lung Tumors: GTVs within 2cm of the proximal bronchial tree (carina, right and left main bronchia, right and left upper lobe bronchi, intermedius bronchus, right middle lobe bronchus, lingular bronchus right and left lower lobe bronchi.
 - Lung Peripheral: metastases within the lung parenchyma with GTV outside of the proximal bronchial tree as described above.
 - Mediastinal Lymph Nodes: GTV arising within the anatomic space between the lungs, above the diaphragm, and below the thoracic inlet at the level of the top of the sterna notch.
 - Head and Neck: GTV occurring within cervical lymph node levels I-VI and/or retropharyngeal spaces, oral cavity, oropharynx, nasopharynx, hypopharynx, para-nasal sinuses, nasal cavity, and parotid gland/space.
 - Liver: GTV arising within the liver.
 - Spine: metastases will be assigned to the spinal/paraspinal site if the GTV arises within the vertebral bodies expanded by 1cm.
 - Osseous: GTV arising within an osseous structure, part of the axial skeleton, not included in the spinal definition.
 - Abdominal-Pelvic: GTV arising within the anatomic space defined by the diaphragm superiorly, the genitourinary diaphragm inferiorly include the peritoneal and retroperitoneal spaces, not including liver, osseous, or spinal metastases.
- While no specific size constraint exists, the treating radiation oncologist must have a reasonable expectation that the dose constraints outlined in the appendix will be met; if, during planning, dose constraints to outlined normal tissue structures are exceeded, the treating radiation oncologist must receive permission of the study PI ([name]) prior to proceeding with treatment. If permission is not obtained, the patient will be withdrawn from the study.
- In instances where there is a metastatic or recurrent lesion that is either causing symptoms or on the precipice of doing so, the treating radiation oncologist should select this lesion for irradiation.
- Every effort should be made to choose a target lesion outside of a previously irradiated site. However, the treated lesion can be a lesion that was previously

irradiated as long as prior radiation was at least 6 months before the projected first fraction of SBRT and as long as re-irradiation dose constraints as outlined in appendix are met. In cases of re-irradiation, if the re-irradiation dose constraints outlined in the appendix are exceeded, the patient will be withdrawn from the study.

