13.1 CRITERIA FOR REMOVAL FROM STUDY

Treatment with Nivolumab will continue until RECIST 1.1-defined progression, unacceptable toxicity, failure to obtain PI approval for radiation plans that exceed normal tissue dose constraints as outlined in the appendix, or withdrawal of consent.

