14.0 BIOSTATISTICS

11.1 Primary Objective

The primary objective of this study is to compare best overall response (BOR) rate by 96 weeks as determined by the investigator using RECIST 1.1 criteria between patients receiving Nivolumab and SBRT and those receiving Nivolumab alone. BOR rate is defined as the number of patients randomized to a given arm with a best overall response of complete response (CR) or partial response (PR) of non-irradiated lesions divided by the total number of patients randomized to the given arm. In order to ascertain this endpoint, efforts will be made so that patients will be followed for 96 weeks or until progression of disease (and treatment cessation), whichever comes first.

Based upon an estimated ORR of 15% in a PD-L1 unselected population in the Nivolumab alone arm (based on data from Siewert, et al; see background) and an ORR of 45% in the Nivolumab and SBRT arm, the enrollment of 54 patients with a two-sample proportion test will provide a one-sided alpha of 0.10 and a power of 0.80. Assuming a 10% drop-out rate, we will enroll a total of 60 patients. Patients will be randomized to the two treatment arms in a 1:1 ratio. Patients will be stratified based upon viral status (virus negative versus virus positive; virus status is defined by EBV (EBER testing) or HPV (p16, HPV ISH, HPV PCR) testing). Assuming a constant enrollment of 3 subjects per month, it would take approximately 20 months to randomize 60 patients. Calculations were completed using software R 3.1.1 and EAST 6.

To ensure eligible endpoints are well defined, a minimum of 6 months of follow up after treatment initiation is required. Patients lost to follow-up prior to 6 months (24 week scan) will be replaced, regardless of response. Patients lost to follow-up between 6 months and 24 months will be included in the ORR calculation.

Secondary objectives:

OS and PFS will be evaluated by the regular survival analysis tools such as Kaplan-Meier and competing risks methods. Comparisons will be conducted between the two arms by the stratified log-rank test and Gray's test.

The DOR will be calculated from the time of response to progression or last follow up and analyzed using the Kaplan-Meier method among patients who showed response.

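### A withdrawal rule applied after randomisation, in Arm 2 only, can drop patients from the ORR analysis set and censor their OS and PFS early

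*Combined protocol and SAP*

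**What the plan says.** **The rule**

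- Section 9.1 places planning after allocation and in one arm: "Arm 2: After randomization, patients will complete CT simulation". The first fraction is due by study day 14.
- Section 9.2.1 (SBRT, Target Selection) says that if normal-tissue constraints are exceeded during planning, "the treating radiation oncologist must receive permission of the study PI" before treating. It continues: "If permission is not obtained, the patient will be withdrawn from the study".
- For a previously irradiated target the same section has no permission step: "if the re-irradiation dose constraints outlined in the appendix are exceeded, the patient will be withdrawn from the study".
- Section 13.1 carries a heading on removal from study, but its sentence lists the reasons for ending nivolumab. One of them is "failure to obtain PI approval for radiation plans that exceed normal tissue dose constraints as outlined in the appendix". The re-irradiation case is not listed there.

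**What governs the analysis**

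- Sections 2.1, 12.1 and 14.0 define the ORR denominator as everyone randomised to the arm.
- Section 14.0 also limits the ORR analysis set to randomised patients with at least 6 months of follow-up after starting treatment, and adds: "Patients lost to follow-up prior to 6 months (24 week scan) will be replaced, regardless of response".
- Section 14.0 analyses PFS and OS in all randomised subjects. Section 12.2.2 censors OS at last contact. Section 12.2.3 gives PFS censoring rules for patients with no follow-up and for those reaching the end of the two-year assessments.
- Section 4.2 (Intervention, Follow-Up Phase) continues scans for patients who stop treatment for a reason other than progression. It does not mention patients withdrawn from the study.

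**The concern.** Randomisation protects the comparison only while both arms are followed and counted alike. Here an event that can occur only after allocation, and only in the SBRT arm, takes a patient off study. An otherwise identical patient in Arm 1 never has a plan drawn up, so stays on study and is counted.

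Two things are at stake. The first is ORR: planning is finished before the first fraction, so these withdrawals should normally fall within about two weeks of the first nivolumab dose, far short of 6 months. If follow-up stops there, the 6-month rule excludes them. The second is PFS and OS: early censoring in one arm is harmful if it is related to prognosis.

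Such a relation is plausible. Section 9.2.1 sets no size limit on the target, directs the radiation oncologist towards lesions that are or soon will be symptomatic, and allows previously irradiated ones. Outside re-irradiation, the outcome also depends on a discretionary permission in an open-label trial.

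**Working it through.** **1. The plan's own figure.** Section 14.0 gives ORR 15% v 45%, one-sided alpha 0.10, power 0.80, 54 patients, and 60 after 10% drop-out. With mean rate 0.30 and difference 0.30:

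n = [1.2816·√(2·0.30·0.70) + 0.8416·√(0.15·0.85 + 0.45·0.55)]² / 0.30² = (0.8306 + 0.5154)² / 0.09 = 20.1 per arm, so 21 per arm and 42 in all.

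With continuity correction: n/4·[1 + √(1 + 4/(n·0.30))]² = 26.4, so 27 per arm and **54** in all. Then 54/0.90 = **60**. The stated size reproduces, with the corrected formula. The plan calls its test a two-sample proportion test and does not say whether the analysis is corrected, so both versions are shown below.

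**2. Following one patient through the sections.** A patient in Arm 2 starts nivolumab on day 1. The plan exceeds the constraints and permission is not given.

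| Question | Answer in the documents |
|---|---|
| Still on study? | No (9.2.1) |
| Are scans continued? | Yes if only treatment was stopped (4.2); not stated for study withdrawal |
| In the ORR denominator? | Yes by 2.1, 12.1 and the definition in 14.0; no by the 6-month set in 14.0 if follow-up ends |
| Replaced? | Only if withdrawal counts as loss to follow-up; not stated |
| In the PFS and OS set? | Yes (14.0). OS is censored at last contact; for PFS, no rule fits a patient who leaves part-way |
| In the safety set? | Yes; 14.0 gives withdrawal before radiation as its example |

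So the plan foresees this patient, but settles only the safety analysis.

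**3. Effect on the ORR test.** The withdrawal frequency is not in the documents, so a share f of Arm 2 is assumed. Worst case: true ORR is 15% in both arms, every withdrawn patient would have been a non-responder, and each is replaced, so that 30 per arm are analysed. The apparent Arm 2 rate is 0.15/(1 − f). Exact enumeration of two binomials, rejecting when the pooled z exceeds 1.2816, gives:

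| f | Arm 2 rate | Uncorrected z | Continuity-corrected z |
|---|---|---|---|
| 0 | 15.0% | 10.7% | 5.5% |
| 5% | 15.8% | 12.4% | 6.5% |
| 10% | 16.7% | 14.4% | 7.7% |

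Ten per cent is 3 of 30, which would alone use up the plan's whole drop-out allowance for that arm.

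If withdrawn patients would have responded at 7.5% rather than 0%, the Arm 2 rate is (0.15 − 0.075f)/(1 − f), and the uncorrected figures fall to 11.5% at f = 5% and 12.5% at f = 10%. If they would have responded at 15%, the Arm 2 rate stays at 15% and there is no inflation.

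**4. Effect of keeping them.** Suppose 3 of 30 stay in the denominator as non-responders. The 45% becomes 0.45·27/30 = 40.5%, and power (normal approximation, uncorrected) goes from 0.908 to 0.832. Excluding them without replacement would leave 0.895.

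**The case against.** Several points on the other side stand.

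- **The trigger is narrow.** A reader might infer that any plan missing a constraint means withdrawal. The documents do not say that: outside re-irradiation the PI can permit treatment, and sites are asked to avoid previously irradiated targets where they can.
- **Both arms are screened first.** Section 6.2 requires, before randomisation, a lesion judged suitable and likely to meet the Section 9.2.1 criteria. Failures should be few. A 20% withdrawal share, at which the worst case reaches 19.7% uncorrected or 11.2% corrected, has no basis in the documents.
- **PFS and OS records are not deleted.** A reader might infer that these data are removed. Section 14.0 keeps all randomised patients in those sets. The risk is early censoring in one arm, and only if follow-up stops.
- **Follow-up may continue.** Section 13.1 treats the event as a reason to end nivolumab, and Section 4.2 then continues scans and survival contact. That reading is possible, but Section 9.2.1 says twice that the patient leaves the study, and nothing extends Section 4.2 to such patients.
- **Replacement is inferred**, and the 6-month rule itself applies to both arms. But this particular route into it exists only in Arm 2.

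It could also be said that repairing the ORR population definition would be enough. It would restore the denominator, but not scans or survival data that were never collected.

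**Conclusion.** The point holds in a limited form. The plan contains a post-randomisation withdrawal rule that can operate only in Arm 2. Combined with the 6-month ORR set, it can take patients out of one side of the primary comparison, contrary to the plan's own all-randomised denominator. It can also censor OS and PFS early in that arm.

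The direction is conditional. A reader might conclude that poorer-prognosis patients are being removed to the benefit of SBRT. No section links constraint failure, which concerns one lesion and its neighbouring organs, to response in the non-irradiated lesions; the link is plausible only.

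The size is modest. With 5% to 10% of Arm 2 withdrawn, the worst case adds about 2 to 4 percentage points to the false-positive rate with the uncorrected test, or 1 to 2 points with the corrected test, which stays below the nominal 0.10. These figures assume the withdrawal share, zero response among those withdrawn, and full replacement. Under equal prognosis the inflation is zero. The rule merits changing because the mechanism is written into the plan and is cheap to remove, not because a large bias has been shown.

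**What to change.** In both places in Section 9.2.1, separate what happens to treatment from what happens to follow-up. State that a patient who does not receive protocol SBRT for dosimetric reasons:

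- remains on study for scheduled scans, safety and survival follow-up unless consent is withdrawn;
- is analysed in Arm 2 in the all-randomised ORR denominator, as a non-responder if no response is documented;
- is not replaced;
- has the reason for not receiving SBRT recorded.

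Then reconcile Sections 4.2 (Follow-Up Phase), 9.2.1, 13.1 and 14.0 with one another, including whether the re-irradiation case belongs in 13.1 and whether protocol-mandated withdrawal counts as loss to follow-up. No position is taken here on the dose constraints or on whether nivolumab continues.

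The cost is protocol wording, follow-up of a few more patients, and a somewhat lower Arm 2 ORR and power: about 0.91 to 0.83 if 3 of 30 are counted as non-responders (uncorrected test), and less than that if any of them has a documented response.

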2.1 OBJECTIVES AND SCIENTIFIC AIMS

Primary Objective:

- To compare objective response rate (ORR) during the first 2 years of treatment as determined by the investigator using Response Evaluation Criteria in Solid Tumors (RECIST) 1.1 criteria between patients receiving Nivolumab and SBRT to those receiving Nivolumab alone. The ORR is defined as the number of patients randomized to a given arm with a best overall response (BOR) of complete response (CR) or partial response (PR) in non-irradiated lesions during the first 96 weeks after treatment initiation divided by the total number of patients randomized to the given arm.

Secondary Objectives:

- To compare Overall Survival (OS) of Nivolumab and SBRT to Nivolumab alone.
- To compare Progression Free Survival (PFS) of Nivolumab and SBRT to Nivolumab alone.
- To compare duration of response (DOR) between the Nivolumab alone arm and Nivolumab + SBRT arm.
- To compare treatment-related Adverse Events (tr-AE) of Nivolumab and SBRT to Nivolumab alone using Common Terminology Criteria for Adverse Events version 4.0 (CTCAE v 4.0).
- To evaluate cancer-specific health related quality-of-life using the EORTC-QLQ C-30.

Exploratory Objectives:

- Evaluation of tumor tissue PDL1 expression via IHC and its correlation with response.
- Evaluate of peripheral blood mononuclear cell composition and its correlation with response
- Evaluation of soluble PD-1 and PD-L1 and its correlation to response.
- Evaluation of neo-antigen expression (optional) and its correlation to response.

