- Positive test for hepatitis B virus surface antigen or hepatitis C virus ribonucleic acid indicating acute or chronic infection.
- Known history of testing positive for HIV or known AIDS.
- Any grade 4 laboratory abnormalities.

Allergies and Adverse Drug Reaction

- History of allergy to Nivolumab components
- History of severe hypersensitivity reaction to any monoclonal antibody.

Prohibited or Restricted Treatments

The following medications are prohibited during the study:

- Immunosuppressive agents (except to treat a drug-related adverse event).
- Systemic corticosteroids > 10 mg daily prednisone equivalent save for exclusion outlined in the below paragraphs.
- Any concurrent chemotherapy, hormonal therapy, immunotherapy, or investigational agents for treatment of cancer.

Supportive care for disease-related symptoms may be offered to all subjects on the trial.

Permitted Therapies During Study

In either arm, if the investigator deems it medically necessary, non-target lesions can receive conventionally dosed, palliative radiation therapy. Palliative radiotherapy is not permitted within 24 weeks of first study treatment. Subjects receiving palliative radiation therapy will be considered to have had unequivocal progression of disease. Administration of Nivolumab to subjects who received palliative radiation should follow guidelines specified for treatment beyond disease progression. Any subsequent responses to therapy after the receipt of palliative radiation will not be counted towards the calculation of the primary endpoint, but patients who receive palliative radiation who remain on Nivolumab will have continued study-mandated scans until a 2nd progression event or 96 weeks, whichever occurs earlier.

Other permitted therapies include topical, ocular, intra-articular intranasal and inhalational corticosteroids. Adrenal replacement steroid doses including doses > 10 mg daily prednisone are also permitted.

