12.0 CRITERIA FOR THERAPEUTIC RESPONSE/OUTCOME ASSESSMENT

12.1 Primary Endpoint:

To compare overall response rate (ORR) in non irradiated lesions during the first 96 weeks after treatment initiation as determined by the investigator using Response Evaluation Criteria in Solid Tumors (RECIST) 1.1 criteria between patients receiving Nivolumab and SBRT to those receiving Nivolumab alone. ORR rate is defined as the number of patients randomized to a given arm with a best overall response (BOR) of complete response (CR) or partial response (PR) divided by the total number of patients randomized to the given arm.

To serially evaluate tumor response to therapy, it is necessary to estimate the overall tumor burden at baseline and use this as a comparator for subsequent measurements. Measurable disease is defined by the presence of at least one measurable tumor lesion. At baseline, tumor lesions/lymph nodes will be categorized as measurable or nonmeasurable.

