12.1.1 Measurable Lesions

Of note, for purposes of this study, irradiated lesions are not considered measurable.

Measurable lesions must be accurately measured in at least one dimension (longest diameter in the plane of the measurement to be recorded) with a minimum size of:

- 10mm by CT/MRI scan
- Malignant lymph nodes: to be considered pathologically enlarged and measurable, a lymph node must be ≥ 15 mm in short axis when assessed by CT scan. At baseline and in follow-up, only the short axis will be measured and followed.

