12.1.6 Baseline Documentation of "Target" and "Non-Target" Lesions

12.1.6.1 Target Lesions

When more than one measurable lesion is present at baseline all lesions up to a maximum of five lesions total representative of all involved organs should be identified as target lesions and will be recorded and measured at baseline.

Target lesions should be selected on the basis of their size, be representative of all involved organs, and should lend themselves to reproducible repeated measurements.

A sum of diameters (longest for non-nodal lesions, short axis for nodal lesions) for all target lesions will be calculated and reported as the baseline sum diameters. If lymph nodes are to be included in the sum, then as noted below, only the short axis is added into the sum. The baseline sum diameters will be used as reference to further characterize any objective tumor regression in the measurable dimension of the disease.

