12.1.6.2 Non-Target Lesions

All other lesions (or sites of disease) including pathological lymph nodes should be identified as non-target lesions and should be recorded at baseline. Measurements are NOT required and these lesions should be followed as “present”, “absent”, or in rare cases, “unequivocal progression”. In addition, it is possible to record multiple non-target lesions involving the same organ as a single item on the case record form.

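### The primary ORR drops the irradiated lesion in Arm 2 only; recording the would-be SBRT lesion for every patient before randomisation would let this usually small imbalance be checked cheaply

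*Combined protocol and SAP*

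**What the plan says.** The endpoint is limited to lesions that were not irradiated. Section 2.1 counts a complete response or "partial response (PR) in non-irradiated lesions during the first 96 weeks after treatment initiation". Section 12.1 gives the aim as "To compare overall response rate (ORR) in non irradiated lesions during the first 96 weeks after treatment initiation". Section 14.0 counts a complete response or "partial response (PR) of non-irradiated lesions divided by the total number of patients randomized to the given arm".

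Section 12.1.1 adds that "for purposes of this study, irradiated lesions are not considered measurable". For measurable disease at baseline, Section 12.1.6.1 says "all lesions up to a maximum of five lesions total representative of all involved organs should be identified as target lesions". Section 12.1.6.2 continues: "All other lesions (or sites of disease) including pathological lymph nodes should be identified as non-target lesions and should be recorded at baseline".

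On the choice of lesion, Section 9.2.1 (Target Selection) says that where a metastatic or recurrent lesion is "either causing symptoms or on the precipice of doing so, the treating radiation oncologist should select this lesion for irradiation". In both arms, eligibility (Section 6.2, inclusion criteria) requires an irradiable lesion and a separate measurable lesion that will not be irradiated. SBRT insurance approval should precede randomisation. CT simulation follows randomisation, in Arm 2 only (Section 9.1). The trial is open label (Section 4.2, Design) and the investigator reads response.

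**The concern.** The trial asks whether SBRT raises response at sites that were not irradiated. Under these rules the SBRT lesion leaves the scoring in Arm 2, while its Arm 1 counterpart stays among the target or non-target lesions and can hold the patient below partial response or trigger PD. The two arms can therefore be scored on different kinds of lesion set even if SBRT has no effect elsewhere.

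No section shown requires one would-be SBRT lesion to be recorded for each patient before randomisation, or a matching lesion to be left out in Arm 1. The variable list in Section 16.1 names no such item. The eligibility checklist mentioned in Section 15.2 and the case report forms are not among the documents, so this is a statement about what is shown.

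At stake is attribution: part of a higher Arm 2 ORR could come from the scoring rule and not from an abscopal effect. Without a recorded lesion, the effect can only be bounded roughly afterwards, by leaving out candidate lesions in turn. The lesion itself can then no longer be identified free of knowledge of arm or outcome.

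**Working it through.** **1. The plan's own figure.** Inputs from Section 14.0: 15% against 45%, one-sided alpha 0.10, power 0.80, 1:1 allocation. The mean proportion is 0.30.

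- Pooled formula: n = [1.2816·√(2·0.30·0.70) + 0.8416·√(0.15·0.85 + 0.45·0.55)]² / 0.30² = (0.8306 + 0.5154)² / 0.09 = 20.1 per arm.
- Continuity correction: n' = (n/4)·[1 + √(1 + 4/(n·0.30))]² = 26.4, rounded up to 27 per arm, 54 in total.
- Dropout: 54 / 0.90 = 60.

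The stated 54 and 60 are reproduced, so the sample size is not in error.

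**2. How the arms can diverge.** Take two equal lesions, the minimum number for entry. If the index lesion is unchanged and the other shrinks by 30%, the sum falls by 30%/2 = 15%: stable disease in Arm 1. Scored on the other lesion alone, it is a partial response in Arm 2. If the index lesion disappears and the other is unchanged, the sum falls by 100%/2 = 50%: partial response in Arm 1, stable disease in Arm 2. Either direction is possible.

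**3. Size with no true SBRT effect.** The documents give no lesion-level data, so everything here is an assumption. Model: 400,000 simulated patients per setting; log-normal lesion change with SD 0.4, 0.6 or 0.8; within-patient correlation 0.5 or 0.8; log-normal baseline diameters (SD 0.5) independent of change. Response means a summed diameter of at most 0.7 of baseline with no lesion above 1.5 times baseline, at a single time point. The mean is set so that ORR on all lesions is 15%; one lesion is then dropped and the patient rescored.

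| Lesion dropped in Arm 2 | Null Arm 2 ORR |
|---|---|
| Random choice, 2 lesions | 16.6–20.4% |
| Random choice, 3 lesions | 15.6–17.5% |
| Random choice, 5 lesions | 15.2–16.2% |
| All 18 settings above | 15.2–20.4%, median about 16.4% |
| Random choice, 6 or 8 lesions, target slot refilled to five | 15.0–15.9%, median 15.1% |
| Random choice, 2–5 lesions, kept as non-target able to trigger PD | 15.1–18.8%, median 15.6% |
| Weak tilt (r = 0.3) to worse responders, 2–5 lesions | 15.7–22.8% |
| Weak tilt to better responders, 2–5 lesions | 14.4–17.9% |
| Weak tilt to better responders, 6 or 8 lesions | 14.0–14.9% |

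Only 3 of the 18 neutral settings exceed 18%, all with two lesions and correlation 0.5. A neutral drop raises ORR because a sum over fewer lesions varies more around a threshold that few patients reach, and fewer lesions can trigger PD.

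A second model (SD 0.5, correlation 0.3 to 0.7, no single-lesion progression rule, random or largest lesion dropped) gives 17.5–21.8% with two lesions, 15.9–18.0% with three, 15.6–16.9% with four and 15.2–15.9% with six.

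**4. False-positive rate.** With 30 per arm and Arm 1 at 15%, the rate is the sum, over all pairs (x, y) that the one-sided 0.10 test rejects, of Bin(x; 30, 0.15)·Bin(y; 30, p₂).

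| Arm 2 null ORR, p₂ | Fisher | Uncorrected z |
|---|---|---|
| 15% | 0.055 | 0.107 |
| 16% | 0.068 | 0.128 |
| 17% | 0.082 | 0.152 |
| 18% | 0.099 | 0.177 |
| 20% | 0.137 | 0.233 |

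Fisher stays below 0.10 in 15 of the 18 neutral settings. Section 14.0 does not say which two-proportion test is meant, so the applicable column is open.

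**The case against.** The strongest defence is that the contrast is intended. Section 3.4 sets response at unirradiated sites against systemic response on nivolumab alone, and the endpoint follows from that. Scoring all of Arm 1's unirradiated disease is a coherent reading. The median neutral shift is about 1.4 points (16.4 − 15), beside a planned difference of 30. The eligibility and insurance rules make it likely that a candidate site is considered before randomisation in both arms. The target sums need not differ at all if the lesion is non-measurable (Section 12.1.3), cannot be a target because of earlier radiotherapy (Section 12.1.5), or is replaced because there are more than five measurable lesions.

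All of this stands, and it keeps the point modest. It does not deal with the unequal lesion sets, and considering a site is not the same as recording it.

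Three stronger readings are tempting, and the documents do not support them.

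- *The symptomatic-lesion rule removes the worst lesion and so favours Arm 2.* The rule applies only where such a lesion exists, and no section says these lesions respond worse.
- *The effect could never be examined afterwards.* Target lesions are measured and non-target lesions recorded at baseline, so a rough bound is possible.
- *The palliative radiotherapy rule widens the gap*, since "Subjects receiving palliative radiation therapy will be considered to have had unequivocal progression of disease" (Section 6.2, Permitted Therapies). That rule covers either arm, only non-target lesions, and only after 24 weeks. In an Arm 1 patient with five or fewer measurable lesions, a measurable symptomatic lesion would normally be a target, so the rule does not reach the patients in whom the modelled effect is largest.

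**Conclusion.** The asymmetry is in the text: the SBRT lesion is dropped in Arm 2 only, and nothing shown has a matching Arm 1 lesion recorded or left out. This is a worthwhile, cheap improvement and not a defect that undermines the primary comparison.

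Under neutral choice the null Arm 2 ORR is about 15.2–20.4% against 15%. It matters mainly for patients with two lesions and is negligible with six or more. These figures rest on assumed lesion numbers, variability and correlation, and ignore confirmation of response. The direction is unproven and can reverse.

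A smaller wording problem goes with it. Sections 2.1, 10.1.2, 12.1 and 14.0 point to full exclusion of the SBRT lesion, while Sections 12.1.1, 12.1.2 and 12.1.6.2 can be read as keeping it as a non-target lesion that can trigger PD.

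**What to change.** 1. Before randomisation, record for every patient the one lesion that would be irradiated if assigned to Arm 2, together with the RECIST target lesions.
2. In Section 12.1, state how the Arm 2 SBRT lesion is scored, consistently with Sections 2.1, 12.1 and 14.0, and reconcile this with Sections 12.1.1, 12.1.2 and 12.1.6.2.
3. Keep the primary analysis. Prespecify as a key sensitivity analysis an ORR with the index lesion left out of target, non-target and PD scoring in both arms, on scans already collected.
4. In that analysis, count patients whose first PD concerns the index lesion only. Show results with them as non-responders and with their last available non-index assessment.
5. Report how often the lesion treated differs from the one recorded.

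This concerns recording and scoring only, not which lesion is treated.

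The cost is one field, some wording and one extra analysis, with three limits.

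- The correction is partial, because study scans stop at progression for patients who come off nivolumab (Section 4.2, Intervention; Sections 10.1.2 and 13.3). In the model with random choice and 2–5 lesions, index-only PD affects 1.8–12.7% of Arm 1, median 4.6% (30 × 0.018 to 30 × 0.127, or about 0.5 to 3.8 patients). Non-index responders among them are 0–3.8% of Arm 1, at most about one of 30, so the two results in item 4 should lie close together.
- The index-excluded Arm 1 ORR is less comparable with published rates; the primary analysis still gives the all-lesion figure.
- If the index-excluded control ORR exceeds 15%, power against 45% falls. At 27 per arm, Fisher (uncorrected z) power is 0.807 (0.886) at 15%, 0.749 (0.841) at 17% and 0.656 (0.763) at 20%. At 30 per arm and 20% it is 0.720 (0.809).
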